1 INTRODUCTION

Patients with chronic kidney disease (CKD) have limited treatment options with current standard of care (SoC). The mechanisms of action of zibotentan and dapagliflozin are different and the outcome of combined treatment is expected to be synergistic, since the main biological effects of zibotentan are to block endothelin-1-dependent vasoconstriction and hypertension, to increase renal blood flow, and to reduce podocyte loss, vascular stiffness, endothelial dysfunction, fibrosis and inflammation; and of dapagliflozin are to inhibit sodium-glucose co-transporter 2 (SGLT2) to increase urinary excretion of glucose, sodium and water, to improve metabolic health, decrease vascular stiffness, improve endothelial function, and decrease oxidative stress and inflammation. Both mechanisms show efficacy in reducing albuminuria in CKD. However, unlocking the renal benefit of endothelin antagonists requires mitigation of their potential to cause fluid retention and to increase the risk of developing heart failure (HF) in some patients.

The primary objective of this study is to evaluate the effect of zibotentan 1.5 mg and dapagliflozin 10 mg in combination, compared to dapagliflozin 10 mg monotherapy, on urinary albumin to creatinine ratio (UACR). The secondary objectives are to determine the change in UACR for zibotentan 0.25 mg combined with dapagliflozin 10 mg versus dapagliflozin 10 mg monotherapy, and the change in office systolic and diastolic blood pressure (BP) for doses of zibotentan combined with dapagliflozin 10 mg versus dapagliflozin 10 mg monotherapy, to characterise the dose-response relationship of the different zibotentan/dapagliflozin doses and the UACR reduction, and to determine the effect of zibotentan and dapagliflozin in combination versus dapagliflozin 10 mg on eGFR.

This Statistical Analysis Plan (SAP) documents the variables to be analysed and the methods of analyses planned. The analyses of the following variables will be reported outside the clinical study report (CSR) and are therefore outside the scope of this SAP:

- Plasma concentration of zibotentan metabolites
- Blood and urine biomarkers relevant to cardiorenal mechanisms, inflammation, and fibrosis
- Genes/genetic variation that may influence response to treatment

An electronic case report form (eCRF) will be used to capture participant data into a secure, validated database. The following data are captured outside the eCRF and will be transferred electronically into the database periodically during the study:

- Safety laboratory data
- Electrocardiogram (ECG) data
- Plasma concentration of zibotentan and dapagliflozin
- Pharmacodynamic (PD) urine and blood samples
- Bioimpedance spectroscopy (BIS)
- Ambulatory blood pressure monitoring (ABPM)
- Hand-held electronic diary (eTablet) or paper diary (information may be entered in the eCRF based on the paper diary)
- Protocol deviations

The analyses described in this SAP are based upon the following study documents:

- Study Protocol, Amendment 2 (05 APR 2022)
- electronic Case Report Form, Version 8.0 (09 AUG 2022)

2 STUDY OBJECTIVES

2.1 Primary Objective

Primary Objective	Estimand Description/Endpoint

 • To evaluate the effect of zibotentan 1.5 mg/dapagliflozin 10 mg versus dapagliflozin 10 mg monotherapy on UACR. 	
 • Change in log-transformed UACR from baseline to Week 12. 
The primary estimand is a hypothetical estimand such that the treatment effect is quantified in the optimal situation where any potential confounder is avoided. The population of interest is the Full Analysis population. Participants will be included in the analysis if they have a non-missing baseline and at least one post-treatment visit UACR measurement. For the intercurrent events, if a participant dies, prematurely discontinues study treatment, or uses prohibited medication, the UACR data are treated as missing after the event and no imputation is performed. The summary measure being evaluated is the geometric mean reduction difference of UACR from baseline to Week 12.

Abbreviations: AE = adverse event; UACR = urinary albumin to creatinine ratio.

2.2 Secondary Objectives

Secondary Objectives ^a	Endpoints

 • To evaluate the effect of zibotentan 0.25 mg/dapagliflozin 10 mg versus dapagliflozin 10 mg monotherapy on UACR. 	
 • Change in log-transformed UACR from baseline to Week 12.

 • To determine the change in office systolic and diastolic BP for doses of zibotentan combined with dapagliflozin 10 mg versus dapagliflozin 10 mg monotherapy. 	
 • Change in BP from baseline (Visit 2) to Week 12.

 • To characterise the dose-response relationship (relationship between different doses of zibotentan/a fixed dose of dapagliflozin and UACR reduction). 	
 • Change in log-transformed UACR from baseline to Week 12.

 • To determine the effect of different doses of zibotentan and dapagliflozin 10 mg in combination versus dapagliflozin 10 mg monotherapy on eGFR. 	
 • Change in eGFR from baseline to Week 1. • Change in eGFR from baseline to Week 12. • Change in eGFR from baseline to Week 14. • Change in eGFR from Week 1 to Week 12.

Abbreviations: BP = blood pressure; eGFR = estimated glomerular filtration rate; UACR = urinary albumin to creatinine ratio

^a The estimand for the secondary objectives is defined with the same approach as for the primary objective.

2.3 Safety Objective

Safety Objective	Measurements

 • To assess the safety and tolerability of all doses of zibotentan combined with dapagliflozin 10 mg and dapagliflozin 10 mg monotherapy. 	
 • AEs/SAEs/DAEs. • Vital signs. • Clinical laboratory tests. • 12-lead ECG assessment. • Echocardiography assessment. • Event of special interest (changes in fluid-related measures).

Abbreviations: AE = adverse event; DAE = adverse event leading to the discontinuation of study intervention; ECG = electrocardiogram; SAE = serious adverse event.

2.4 Exploratory Objectives

Exploratory Objectives	Endpoints

 To assess the pharmacokinetics of different doses of zibotentan and of dapagliflozin 10 mg in plasma. 	
 Plasma concentrations of zibotentan and dapagliflozin.

 Exploratory analysis of zibotentan metabolites. 	
 Plasma concentration of zibotentan metabolites. 
Results from this analysis will not be reported in the CSR.

 To assess body weight changes in response to different doses of zibotentan and dapagliflozin 10 mg in combination versus dapagliflozin 10 mg monotherapy. 	
 Change in body weight, as measured at the study site, throughout the interventional period.

 To explore the relationships between zibotentan dose/exposure and safety/PD variables. 	
 Dose/exposure of zibotentan relative to safety and PD variables. 
Safety/PD variables include blood assessment for NT-proBNP, BNP, creatinine, and cystatin C, and urine assessment of albumin and creatinine.
 
Results for NT-proBNP will not be reported in the CSR.

 To assess the effect of zibotentan and dapagliflozin in combination versus dapagliflozin 10 mg monotherapy on plasma/serum K⁺, Na⁺, uric acid, BUN, fasting plasma glucose, haematocrit, haemoglobin, ET-1, ELDP, CT-proET-1, and copeptin levels. 	
 Change in plasma/serum concentrations of K⁺, Na⁺, uric acid, BUN, fasting plasma glucose, haematocrit, haemoglobin, ET-1, ELDP, CT-proET-1, and copeptin levels over time during the study. 
Results for ET-1, ELDP, CT-proET-1 and copeptin levels will not be reported in the CSR.

 To assess the effect of zibotentan and dapagliflozin in combination versus dapagliflozin 10 mg monotherapy on cardiovascular biomarkers in blood. 	
 Evaluation of changes in cardiovascular biomarkers in blood (NT-proBNP and BNP) over time during the study. 
Results for NT-proBNP will not be reported in the CSR.


 To assess the effect of zibotentan and dapagliflozin in combination versus dapagliflozin 10 mg monotherapy on body fluid volume and distribution status. 	
 Evaluation of changes in body fluid volume and distribution over the time course of the study. Change in total body water, extracellular water and intracellular water volumes. 
Results will be obtained from using bioimpedance spectroscopy.

Exploratory Objectives	Endpoints

 • Optional: collect and store plasma, serum, and urine samples for potential future exploratory research aimed at exploring biomarkers involved in PK, PD, safety and tolerability related to zibotentan and dapagliflozin in combination versus dapagliflozin monotherapy or related to cardiorenal diseases. 	
 • Evaluation of changes in blood and urine biomarkers relevant to cardiorenal mechanisms, inflammation, and fibrosis over the time course of the study. 
Results from this future analysis will not be reported in the CSR.

 • Optional: collect and store blood samples for genetic research (according to each country’s local and ethical procedures). 	
 • Exploratory research into genes/genetic variation that may influence response to treatment. 
Results from this optional genetic research will not be reported in the CSR.

Abbreviations: BNP = B-type natriuretic peptide; BUN = blood urea nitrogen; CSR = clinical study report; CT-proET-1 = C-terminal pro-endothelin-1; ELDP = endothelin-like domain peptide; ET-1 = endothelin-1; K⁺ = potassium; Na⁺ = sodium; NT-proBNP = N-terminal pro-B-type natriuretic peptide; PD = pharmacodynamics; PK = pharmacokinetics.

3 INVESTIGATIONAL PLAN

3.1 Overall Study Design and Plan

This is a Phase 2b, multicentre, randomised, double-blind, active-controlled, parallel group dose-ranging study to assess the efficacy, safety and tolerability of zibotentan and dapagliflozin in participants with CKD with eGFR ≥ 20 mL/min/1.73 m², and UACR ≥ 150 mg/g and ≤ 5000 mg/g.

The study will be conducted in approximately 220 sites in North America, South America, Africa, Asia/Pacific, and European countries.

Participants will be randomised to 12 weeks of treatment plus 2 weeks follow-up, as shown in [Figure 1](#). All the variables will be collected (eCRF and third party vendor data) to verify the inclusion and exclusion criteria and additional demographic data such as race/ethnicity, serum creatinine, and height.

Participants who meet the eligibility criteria will be randomised to study treatments in addition to receiving background local SoC therapy. To ensure blinding to treatment and zibotentan dose, daily dosing will consist of one dapagliflozin tablet, containing dapagliflozin 10 mg and one zibotentan capsule containing zibotentan 1.5 mg, zibotentan 0.25 mg or placebo.

A total of 495 participants will be randomised into this study, including participants randomised under the earlier study design. Four hundred and fifteen (415) participants will be randomised to have the following number of participants in the main analysis (marked as M in [Table 4](#)):

- Zibotentan 0.25 mg + Dapagliflozin 10 mg once daily, 83 participants
- Zibotentan 1.5 mg + Dapagliflozin 10 mg once daily, 166 participants
- Dapagliflozin 10 mg once daily, 166 participants

Participants who were previously randomised cannot be re-randomised.

Participants will be stratified by diabetes (diabetic kidney disease [DKD] versus non-diabetes mellitus [non-DM] CKD) and baseline eGFR (below or equal versus above 45 mL/min/1.73m²) at the time of

randomisation to ensure an approximate balance between treatment arms within each sub-population. The strata are:

- Stratum 1: DKD participants with $eGFR \leq 45$ mL/min/1.73m².
- Stratum 2: DKD participants with $eGFR > 45$ mL/min/1.73m².
- Stratum 3: non-DM CKD participants with $eGFR \leq 45$ mL/min/1.73m².
- Stratum 4: non-DM CKD participants with $eGFR > 45$ mL/min/1.73m².

The number of randomised participants in each stratum will be monitored to ensure the non-DM CKD subpopulation is approximately a minimum of 30% and a maximum of 50% of the total number of participants randomised.

[figure not shown]
A first administrative interim analysis may be performed when 50% of participants have completed 6 weeks of treatment or at a time selected by the sponsor. A second administrative interim analysis may be performed after 100% of participants have completed the 6 weeks of treatment or at a time selected by sponsor / percentage of participants with a planned week 6 visit before data cut selected by sponsor. For further details on the interim analysis, see Section 4.13.

For each participant, the total duration of participation will be approximately 17 to 19 weeks. The screening period can be up to approximately 4 weeks in duration prior to randomisation. The first dose will be taken after randomisation at the baseline visit on Day 1. In addition to the baseline visit, the participant will visit the clinic 5 times during the following 12 weeks of treatment. Approximately 2 weeks after the last dose, the participant will visit the clinic again for a follow-up assessment.

The primary objective is to evaluate the effect of zibotentan 1.5 mg/dapagliflozin 10 mg as assessed by change from baseline in (log-transformed) UACR at Week 12, when compared to dapagliflozin 10 mg monotherapy as defined in Section 4.10.2.

[figure not shown]
The study schedule of assessments (SoA) can be found in [Appendix A: Schedule of Activities](#).

Figure 1 Study Schema

First administrative interim analysis when 50% of participants have reached 6 weeks of treatment.

Second administrative interim analysis when 100% of participants have reached 6 weeks of treatment.

DAPA = dapagliflozin; N = numbers of participants; QD = once daily; R = randomisation; SAP = Statistical Analysis Plan; W = week; ZIBO = zibotentan.

3.2 Endpoints

For a full list of all study assessments and the timings of the assessments, see the SoA in [Appendix A: Schedule of Activities](#).

3.2.1 Efficacy Variables

3.2.1.1 Urinary Albumin to Creatinine Ratio (UACR)

The UACR is a key marker for assessing kidney function. The UACR is a ratio between 2 measured substances (urine albumin and creatinine), which estimates 24-hour urine albumin excretion.

The UACR is calculated as follows:

- $UACR (mg/g) = \text{urine albumin (mg/dL)} / \text{urine creatinine (g/dL)}$

Urine samples for the determination of albumin and creatinine levels and calculation of UACR will be collected at the time points described in the SoA in [Appendix A: Schedule of Activities](#).

Spot urine from first morning void will be collected the day after screening and analysed centrally.

For subsequent visits, participants will collect first morning void samples at home on 3 consecutive days. Samples will be analysed centrally.

At each visit (except for screening), the geometric mean of the triplicate UACRs will be computed and used for all analysis of UACR. If any of the samples for a triplicate UACR is missing, then the geometric mean will be calculated based on the available samples for the triplicate.

3.2.1.2 Office/Clinic Blood Pressure Measurement

Blood pressure measurements for participants who receive dapagliflozin monotherapy or different doses of zibotentan combined with dapagliflozin 10 mg will be done during clinic visits at the time points for vital signs indicated in the SoA in [Appendix A: Schedule of Activities](#).

3.2.1.3 Serum Analysis of Creatinine and Cystatin C (eGFR)

Estimated GFR is another measure that is considered as a standard for assessment of kidney function. Estimated GFR is calculated based on serum creatinine values using the widely validated and accepted CKD-EPI equation ([Levey et al, 2009](#)). Blood samples for estimation of serum creatinine (clinical chemistry) are collected at various time points during the course of the study as shown in the SoA in [Appendix A: Schedule of Activities](#).

Estimated GFR, using serum creatinine, is calculated as follows:

- $eGFR \text{ (mL/min/1.73 m}^2\text{)} = 141 \times \min(\text{SCr}/\kappa, 1)^\alpha \times \max(\text{SCr}/\kappa, 1)^{-1.209} \times 0.993^{\text{Age}} \times (1.018 \text{ if female}) \times (1.159 \text{ if Black})$

Where SCr = serum creatinine (in mg/dL), κ is 0.7 for females and 0.9 for males, α is -0.329 for females and -0.411 for males, min indicates the minimum of SCr/ κ or 1, and max indicates the maximum of SCr/ κ or 1.

Alternatively, serum cystatin C provides GFR estimates that are nearly as accurate as serum creatinine adjusted for age, sex, and race thus providing an alternative GFR estimate that is not linked to muscle mass ([Scholtes et al, 2020](#), [Stevens et al, 2008](#)). Blood samples will be collected for measurement of cystatin C, at specified time points as shown in the SoA in [Appendix A: Schedule of Activities](#).

Estimated GFR, using cystatin C, is calculated as follows:

- $eGFR = 133 \times \min(\text{S}_{\text{cys}}/0.8, 1)^{-0.499} \times \max(\text{S}_{\text{cys}}/0.8, 1)^{-1.328} \times 0.996^{\text{Age}} \times 0.932 \text{ [if female]}$

Where S_{cys} is standardized serum cystatin C (in mg/L), min indicates the minimum of $\text{S}_{\text{cys}}/0.8$ or 1, max indicates the maximum of $\text{S}_{\text{cys}}/0.8$ or 1, and age = years.

Estimated GFR calculations using the CKD-EPI formulae (in both ways, based on cystatin C and based on creatinine) will be performed by the central laboratory.

3.2.2 Safety Variables

Safety will be assessed by descriptive analysis of AEs (including serious adverse events [SAEs] and adverse events leading to the discontinuation of study intervention [DAEs]), vital signs, ECGs, laboratory assessments, echocardiography assessments and events of special interest.

Treatment-emergent throughout this document has the meaning of an event such as an AE or laboratory/ECG/vital sign value outside of predefined ranges occurring during on-treatment as defined in Section 4.2.1 and Section 4.11.2.

3.2.2.1 Adverse Events and Serious Adverse Events

Adverse events will be collected after the participant has received the first dose of study intervention throughout the interventional period and including the follow-up period (Visit 8).

SAEs will be recorded from the time of signing of the informed consent form.

3.2.2.2 Physical Examinations

Physical examination, and measurement of weight (analyses will be based on weight measured at the study site, not the home-based monitoring using the digital scales) and height will be conducted at the time points outlined in the SoA in [Appendix A: Schedule of Activities](#). For further information on the physical examinations refer to Section 8.2.1 in the clinical study protocol (CSP).

The only information relating to physical examinations that will be included in the CSR are any associated AEs, the recording and reporting of which are specified in Section 8.3.5 of the clinical study protocol (CSP).

Body weight must be taken and reviewed before continuing treatment at each visit as indicated in the SoA in [Appendix A: Schedule of Activities](#). Weight will be analysed as indicated in one of the exploratory objectives (the third bullet point in the table from Section 2.4).

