1.3 Schedule of Activities
Table 1 Schedule of Activities

Procedure	Screening	Interventional period							Follow-up	Notes	Details in CSP Section/Appendix
		1	2	3	4	5	6	7 (ED)			
Visit	1	2	3	4	5	6	7 (ED)	8			
Week	-4	0	1	3	6	9	12	14			
Day	-28	1	8	22	43	64	84	98			
Day Visit Window	+7/ -14		±1	±2	±2	±2	±2	±3			
Informed consent	X									Section 5.1; Appendix A 3	
Inclusion and exclusion criteria	X	X							Recheck clinical status before randomisation.	Sections 5.1 and 5.2	
Screening in IRT/RTSM	X									Section 6.3	
Randomisation in IRT/RTSM		X							Diaries will be given to the participants and they will be asked to fill in the dose intake information (date and time) at home.	Section 6.3 and 6.4	
Routine clinical procedures											
Demography and baseline characteristics (smoking history and alcohol consumption included)	X									Sections 5.1 and 5.2	
Physical examination	X	X	X	X	X	X	X	X	A complete physical examination will be done at screening, randomisation and Week 12. A brief physical examination will be done at Weeks 1, 3, 6, 9, 14.	Section 8.2.1	

Procedure	Screening	Interventional period							Follow-up	Notes	Details in CSP Section/Appendix
		1	2	3	4	5	6	7 (ED)			
Visit	1							8			
Week	-4	0	1	3	6	9	12	14			
Day	-28	1	8	22	43	64	84	98			
Day Visit Window	+7/ -14		±1	±2	±2	±2	±2	±3			
Medical/ surgical history, which includes substance usage and family history of premature cardiovascular disease	X								Substances: drugs, alcohol, tobacco, and caffeine	Sections 5.1 and 5.2	
Height	X									Sections 5.1, 5.2 and 8.2.1	
Serology (HIV I and II, Hepatitis B surface antigen, Hepatitis C virus antibody, central laboratory)	X								Results need to be available before randomisation.	Section 8.2.4	
FSH/LH and serum pregnancy test (females only, central laboratory)	X								Results need to be available before randomisation.	Section 8.2.4	
Local test for SARS-CoV-2	X								Testing is also required if participants show COVID-19 symptoms during the study.	Section 8.2.4	
Concomitant medication	X	X	X	X	X	X	X	X		Section 6.5	
Efficacy assessments											
Spot urine from first morning void: albumin and creatinine (central laboratory)	X								Results need to be available before randomisation. A single sample for analysis is sufficient at screening.	Section 8.1.1	

Procedure	Screening	Interventional period						Follow-up	Notes	Details in CSP Section/Appendix
		2	3	4	5	6	7 (ED)			
Visit	1						7 (ED)	8		
Week	-4	0	1	3	6	9	12	14		

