
Potential Risk of Clinical Significance	Summary of Data/Rationale for Risk	Mitigation Strategy
Zibotentan (in context of dapagliflozin combination treatment)		
Fluid retention	Peripheral oedema has been very commonly reported in patients receiving zibotentan and tend to develop within a month of commencing the drug. Most cases are mild (CTC Grade 1/2) and tend to resolve with continued dosing.	The potential fluid retention risk from zibotentan will be mitigated by administering a dose lower than 5 mg of zibotentan, combined with the diuretic and natriuretic effects of dapagliflozin. Interim analyses are performed to assess changes in fluid-related measures (weight gain or BNP). Changes in fluid-related measures that meet the defined threshold will be reported as an event of special interest. Discontinuation from study intervention if fluid retention criteria are met (see criteria for weight or BNP in Section 7.1).
Heart failure	Endothelin receptor antagonists have the potential to cause fluid retention and risk of increased incidence of HF.	Exclusion criteria related to presence or risk of HF (see Section 5.2, exclusion criteria #3 to #8 and #30). Administration of a dose lower than 5 mg of zibotentan, combined with the diuretic and natriuretic effects of dapagliflozin. An internal URC of AstraZeneca representatives is set up for this study for ongoing safety monitoring and reviewing the unblinded interim results. In addition to general safety/tolerability, the URC will focus on potential risks related to hospitalisations due to HF. Discontinuation based on heart failure or the defined BNP elevation criteria (see Section 7.1).
Hypotension	Adverse clinical effect of hypotension is largely due to zibotentan's pharmacologically mediated effects of ET receptor antagonism resulting in vasodilation. Hypotension (small reductions in systolic and diastolic BP of approximately 5 mmHg) has been reported with zibotentan but this has usually been asymptomatic.	Monitoring of BP according to the SoA. The URC will focus on potential risks related to hypotension. Discontinuation from study intervention if criteria for symptomatic hypotension is met (systolic BP < 90 mmHg and/or diastolic BP < 60 with symptoms).

Potential Risk of Clinical Significance	Summary of Data/Rationale for Risk	Mitigation Strategy
Other		

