8.2.1 Physical Examinations

Physical examination, and measurement of weight and height will be conducted at the time points outlined in the SoA.

- For weight and height measurements, the participant will be allowed to wear indoor, daytime clothing with no shoes and no coats/jackets and removal of heavy objects from pockets.
- A complete physical examination will include: assessments of general appearance, respiratory, cardiovascular, abdomen, skin, head and neck (including ears, eyes, nose, and throat), lymph nodes, thyroid, musculoskeletal (including spine and extremities) and neurological systems and an assessment of the presence and extent of peripheral (ankle/leg) oedema.
- A brief physical examination will include: assessment of skin (colour, turgor), lungs (breathing rate and breath sounds), cardiovascular system (HR, JVP, sounds), and abdomen (liver and spleen to detect any increase) in addition to vital signs, and an assessment of the presence and extent of peripheral (ankle/leg) oedema.

For information on how AEs based on physical examination findings should be recorded and reported, see Section 8.3.5.

Body weight will be monitored at home using an electronic scale measurement throughout the interventional period as detailed in Section 8.1.3 at the times outlined in the SoA.

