8.3.5 Adverse Events Based on Examinations and Tests

The results from the CSP-mandated laboratory tests and vital signs will be summarised in the CSR.

Deterioration as compared to baseline in protocol-mandated laboratory values, vital signs, ECG parameters, and echocardiography findings should therefore only be reported as AEs if they fulfil any of the SAE criteria, are the reason for discontinuation of treatment with the investigational product, or are considered to be clinically relevant as judged by the investigator (which may include but not limited to consideration as to whether treatment or non-planned visits were required or other action was taken with the study intervention, eg, dose adjustment or drug interruption).

If deterioration in a laboratory value/vital sign is associated with clinical signs and symptoms,

the sign or symptom will be reported as an AE and the associated laboratory result/vital sign will be considered as additional information. Wherever possible the reporting investigator uses the clinical, rather than the laboratory term (eg, anaemia versus low haemoglobin value). In the absence of clinical signs or symptoms, clinically relevant deteriorations in non-mandated parameters should be reported as AE(s).

Any new or aggravated clinically relevant abnormal medical finding at a physical examination, as compared with the baseline assessment, will be reported as an AE unless unequivocally related to the disease under study.

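### Peripheral oedema is examined at all eight visits, but the SAP reports it only as adverse events, so mild oedema may be under-ascertained and change from baseline cannot be seen

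*SAP*

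**What the plan says.** Protocol 8.2.1 puts the same item into both the complete and the brief physical examination: "an assessment of the presence and extent of peripheral (ankle/leg) oedema". The Schedule of Activities places a complete examination at screening, randomisation and Week 12. For the other visits it states: "A brief physical examination will be done at Weeks 1, 3, 6, 9, 14".

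Protocol 2.3.1, Table 2, lists peripheral oedema under the fluid-retention risk of zibotentan: "Peripheral oedema has been very commonly reported in patients receiving zibotentan and tend to develop within a month of commencing the drug". The same entry describes most cases as mild.

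SAP 3.2.2.2 then limits what is reported: "The only information relating to physical examinations that will be included in the CSR are any associated AEs". For how such AEs are recorded, it refers to Protocol 8.3.5, which reads: "Any new or aggravated clinically relevant abnormal medical finding at a physical examination, as compared with the baseline assessment, will be reported as an AE", with the exception "unless unequivocally related to the disease under study".

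**The concern.** The trial makes a repeated, blinded assessment of a sign that its own risk table expects from the drug, and the SAP plans no table of the result. Whether a given case of oedema is reported depends on the investigator's view of its clinical relevance and cause. Mild oedema is most exposed to the relevance judgement, and Table 2 says most cases are mild.

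Two things are at stake. The absolute frequency of oedema at each zibotentan dose may be understated, in a dose-ranging trial whose safety data feed dose selection (SAP 4.10.2.7). In addition, oedema present before the first dose, and improvement or worsening from it, would not be visible by arm.

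**Working it through.** **1. How often oedema is assessed.** Complete examinations: screening, randomisation and Week 12, so 3. Brief examinations: Weeks 1, 3, 6, 9 and 14, so 5. 3 + 5 = 8, which is every scheduled visit. Two of the eight precede treatment or fall on the day it starts, so a baseline status exists.

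**2. What a finding must pass to reach the CSR.** Under Protocol 8.3.5 it must be (a) new or worse than at baseline, (b) clinically relevant, and (c) not unequivocally due to the disease under study. Stable baseline oedema fails (a) by design. Mild oedema may fail (b).

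**3. Comparison with other assessments.** The same section limits AE reporting of mandated laboratory values and vital signs, and gives as the reason that their results are summarised in the CSR anyway. For physical examinations the AE route is also filtered, but SAP 3.2.2.2 removes the summary.

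**4. Other routes in the plan.**

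| Route | Compared or summarised by arm? | Reports the examined oedema? |
|---|---|---|
| AEs reported, elicited or observed (Protocol 8.3.4) | Yes, by SOC and PT | Only if recorded as an AE |
| Narrow-scope SMQ table for oedema and fluid overload (SAP 4.11.2) | Yes | Only if recorded as an AE |
| Event of special interest: BNP, or weight plus body water (SAP 3.2.2.7, 4.11.5.1) | Yes, with incidence rates and relative risk | No, oedema is not a component |
| Weight and body-water volumes (SAP 4.10.4) | Yes | No |
| Vital signs, ECG, echocardiography (SAP 4.11.5) | Yes | No |

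Non-serious AEs are collected only after the first dose (Protocol 8.3.1), so the first two routes cannot show baseline oedema or a shift from it.

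**5. Possible size.** The plan gives no oedema rate or capture fraction, so there is no figure to reproduce, and everything in this step is assumed except the arm size of 166 (SAP 3.1). Let the true rates be p1 (zibotentan 1.5 mg plus dapagliflozin) and p0 (dapagliflozin alone), and let AEs capture a fraction c of cases in both arms. Then:

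- observed risk difference = c(p1 − p0)
- observed relative risk = c·p1 / c·p0 = p1/p0, unchanged

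The last column of the table is power for a two-sided 5% comparison of two proportions. It serves only as an index of sensitivity, since the SAP plans no such test for oedema.

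| True p1 vs p0 | c | Observed rates | Risk difference (points) | Relative risk | Power |
|---|---|---|---|---|---|
| 15% vs 5% | 1.0 | 15% vs 5% | 10 | 3.0 | 0.86 |
| | 0.8 | 12% vs 4% | 8 | 3.0 | 0.77 |
| | 0.6 | 9% vs 3% | 6 | 3.0 | 0.63 |
| | 0.4 | 6% vs 2% | 4 | 3.0 | 0.46 |
| 20% vs 10% | 1.0 | 20% vs 10% | 10 | 2.0 | 0.72 |
| | 0.6 | 12% vs 6% | 6 | 2.0 | 0.48 |
| 10% vs 5% | 1.0 | 10% vs 5% | 5 | 2.0 | 0.41 |
| | 0.6 | 6% vs 3% | 3 | 2.0 | 0.26 |

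Incomplete capture that is equal in both arms lowers absolute rates and sensitivity. It does not distort the ratio.

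**The case against.** The strongest reply is that fluid retention is already well covered. BNP, site weight and bioimpedance are systematic and do not depend on an investigator's attribution. The composite event is compared with dapagliflozin, and changes below its threshold appear in the weight and body-water summaries. Protocol 8.3.4 also gives oedema a second way to become an AE, with no exception for disease-related findings, and a dedicated SMQ table follows. The exception in 8.3.5 needs an unequivocal link to the disease, which is hard to assert for new oedema in a blinded trial whose protocol warns of it. All of this stands, and it limits the point to the examined sign itself. It does not supply an oedema table: the AE routes still depend on recording, and the objective measures contain no oedema component.

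A second reply is that the eCRF is not among the documents, so the field may not exist. Protocol Appendix A 7 says participant data are recorded on the eCRF unless transmitted electronically, which largely answers this. The sponsor should still confirm what is held.

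A reader might also infer that the harm that closed the 5 mg arms is never compared between arms. The documents do not support that. Those arms closed because of the rate of fluid retention events (Protocol 4.3 and Appendix H), and the fluid-related measures are compared or summarised by arm (SAP 4.10.4 and 4.11.5.1).

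**Conclusion.** The point holds as a gap in planned reporting: a targeted safety assessment made at every visit has no planned tabulation, and the AE rule can leave some of its findings out. It is a cheap improvement to the safety reporting and does not touch the primary analysis.

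Under-ascertainment is a risk and has not been shown. Its size rests on assumed rates and an assumed capture fraction. That the relative risk is unaffected rests on equal loss in both arms, which blinding makes plausible but does not guarantee.

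Some stronger readings go beyond the text. The protocol asks for presence and extent and gives no grading scale. It states that "Peripheral oedema has been very commonly reported in patients receiving zibotentan" but does not rank oedema as the commonest harm. A mere suspicion that oedema is due to CKD does not exempt it from AE reporting.

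**What to change.** In SAP 3.2.2.2, replace the AE-only sentence, and add to SAP 4.11.5, on the Safety Analysis Set:

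- oedema presence, and extent where the eCRF holds it, by visit and arm;
- a shift table from baseline to the worst post-baseline assessment, by arm;
- the number and percentage with new or worsened oedema, by arm. A risk difference with a confidence interval versus dapagliflozin is optional, since safety is planned as descriptive.

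Keep the AE, SMQ and event-of-special-interest tables as they are.

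The cost is a few descriptive tables from an examination already scheduled, with no new visit or procedure. The sponsor should confirm which oedema fields the eCRF captures. If extent is missing, tabulate presence only; if neither is captured, state that as a limitation. No change to any dose or stopping rule is implied.
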